TAM	Tumour Associated Macrophage

KEYWORDS

Tumour, Oxygenation, Sensor, Diffuse Reflectance Spectroscopy

STUDY SUMMARY

TITLE	Development and Validation of a Tumour Oxygenation Monitoring Probe
DESIGN	Tumour oxygenation sensor validation using 3D-Printed tissue phantoms
AIMS	To design and validate a novel tumour oxygenation monitoring probe which may be used to monitor response to therapies in cancer, using 3D-printed phantoms
OUTCOME MEASURES	Correlation of sensor oxygenation measurements as compared to gold-standard oxygenation measurements in phantom tissue models
POPULATION	3D printed tissue phantoms, based upon breast and rectal cancer MRIs
ELIGIBILITY	20 Anonymised pre-treatment MRI scans for patients with locally advanced rectal cancer (10 scans) and breast cancer (10 scans) MRIs from patients younger than 18 years of age, or older than 99 years of age will be excluded. MRIs from patient who did not go on to receive neoadjuvant therapy will be excluded
DURATION	1 Year

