1.1.5 A Novel Tumour Oxygenation Monitor using DRS

Tumour oxygenation monitoring has the potential to provide valuable insights into tumour prognostication and management. The Institute for Global Health Innovation plans to develop an implantable tumour oxygenation sensor, providing a novel modality for tumour assessment and

monitoring. This research describes the development and validation of oxygenation sensing probe (Figure 2). Successful development and validation of the probe will be followed by future research to miniaturise and incorporate the technology into an implantable device.

[figure not shown]

Figure 2: A tumour oxygenation monitoring probe using diffuse reflectance spectroscopy.

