1.2 RATIONALE FOR CURRENT STUDY

Overall Research Hypothesis:

- Dynamic tumour oxygenation monitoring can predict treatment response in chemoradiotherapy for rectal and breast cancer.

Current Research Hypothesis:

- A novel-designed tumour oxygenation monitor, utilising diffuse reflectance spectroscopy, can provide accurate tissue oxygenation assessment in tumour phantom models.

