2. STUDY OBJECTIVES

Primary Objective:

- To develop and validate a novel tumour oxygenation monitoring probe which may be used to monitor response to therapies in cancer, using 3D-printed phantoms.

Secondary Objectives:

- Define the correlation between sensor-derived oxygenation measurements and Gold-standard measured oxygenation in 3D-printed tissue phantoms
- Define the spatial resolution of the sensor oxygenation measurements

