3.4 Sensor Measurement Collection

Measurements of oxygenation within the 3D printed phantoms will first be performed using a benchtop spectrometer to provide a “gold standard”. This benchtop system allows for measurements with a high spectral resolution over a broad spectral range, whereas the sensor by necessity is targeted at key wavelengths (Figure 1). The results of these experiments will assess the suitability of the sensor design for monitoring oxygenation in tumours.

[figure not shown]

Figure 3: Schematic demonstrating a 3D printed phantom, TOAST++ simulation, novel monitoring probe and future miniaturised device (left to right)

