3.5 Statistical Analysis

The fraction of the volume of the tumour to which the sensor is sensitive will be expressed as a % of the total volume, and the fraction for each tumour will be expressed as a mean+SD summary statistic.

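### The Statistical Analysis section does not analyse sensor against reference, and the unspecified correlation named as the outcome could not by itself show that the sensor is accurate

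*Combined protocol and SAP*

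**What the plan says.** The Study Summary has a single entry under Outcome Measures: "Correlation of sensor oxygenation measurements as compared to gold-standard oxygenation measurements in phantom tissue models". Section 1.2 states the hypothesis of the present study, that the monitor "can provide accurate tissue oxygenation assessment in tumour phantom models".

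The primary objective in Section 2 is "To develop and validate a novel tumour oxygenation monitoring probe which may be used to monitor response to therapies in cancer, using 3D-printed phantoms". The same section lists two secondary objectives: "Define the correlation between sensor-derived oxygenation measurements and Gold-standard measured oxygenation in 3D-printed tissue phantoms" and "Define the spatial resolution of the sensor oxygenation measurements".

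Section 3.4 names a benchtop spectrometer as the reference and adds that "The results of these experiments will assess the suitability of the sensor design for monitoring oxygenation in tumours". It gives no method or threshold for that judgement.

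Section 3.5, Statistical Analysis, is one sentence. It begins "The fraction of the volume of the tumour to which the sensor is sensitive will be expressed as a % of the total volume" and goes on to a mean and SD across tumours.

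Section 1.1.5 says what a good result leads to: "Successful development and validation of the probe will be followed by future research to miniaturise", with an implantable device as the aim.

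**The concern.** There are two linked problems.

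- **The outcome has no analysis.** Section 3.5 deals with a quantity that is neither listed as an outcome nor named as an objective. It contains no correlation and no sensor-minus-reference difference.
- **The named measure does not answer the question.** Whether a sensor is accurate depends on how far its readings lie from the true values. An ordinary correlation asks only whether the two sets of readings rise and fall together.

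A miscalibrated sensor could therefore score close to 1 and, with no acceptance criterion, be reported as validated and taken forward to miniaturisation. No patient is treated in this study, so what is at stake is whether its conclusion can be relied on.

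**Working it through.** The documents give no target correlation, acceptable error, variability or sample-size calculation, so there is no figure of the plan's own to reproduce. The property at issue is algebraic; the numbers only show its size.

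**Property.** If sensor = a + b × reference with b > 0, then Pearson r and Spearman r both equal 1 for every a and b. Only a = 0 and b = 1 is an accurate sensor.

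**Assumed inputs (none from the documents).** 20 equally spaced reference values from 10% to 90%. Their mean is 50. Their spacing is 80/19 = 4.21, so their SD is 4.21 × √(20 × 21/12) = 24.9 points.

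**Case A: sensor = reference + 15.** r = 1.00, bias +15 at every level.

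**Case B: sensor = 0.5 × reference + 30, no noise.**
- Difference = 30 − 0.5 × reference, which is +25 at 10%, +5 at 50% and −15 at 90%.
- Mean bias is +5.0. SD of differences = 0.5 × 24.9 = 12.45.
- 95% limits of agreement = 5.0 ± 1.96 × 12.45 = −19.4 to +29.4.
- r = 1.00; calibration slope 0.50, intercept 30.
- A true change from 40 to 60 reads as 50 to 60, so 20 points become 10.

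**Case C: as B, plus normal random error (20,000 simulations).**

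| Error SD | Mean r (2.5th–97.5th percentile) | Mean limits of agreement |
|---|---|---|
| 3 points | 0.974 (0.953–0.988) | −20.1 to +30.1 |
| 5 points | 0.931 (0.876–0.969) | −21.2 to +31.2 |

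Because the error in B and C depends on level, limits by level describe it better. With error SD 5, they are +25 ± 1.96 × 5 = +15.2 to +34.8 at 10%, and −15 ± 9.8 = −24.8 to −5.2 at 90%.

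**Dependence on range.** For an unbiased sensor with an assumed error SD of 8 points, r = SD_ref/√(SD_ref² + 8²). This gives 0.53, 0.78, 0.93 and 0.97 for reference SDs of 5, 10, 20 and 30. The same error thus produces a poor or an excellent r according to the levels chosen, and the documents do not state those levels.

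**Precision.** The Study Summary gives 20 scans, 10 rectal and 10 breast. One independent pair per scan is an assumption.
- 95% CI for an observed r of 0.90 = tanh(atanh 0.90 ± 1.96/√(n − 3)). At n = 20 this is tanh(1.472 ± 0.475) = 0.76 to 0.96. At n = 10 it is tanh(1.472 ± 0.741) = 0.62 to 0.98.
- 95% CI half-width for one limit of agreement, in SDs of the differences = t × √(1/n + 1.96²/(2(n − 1))), assuming roughly normal differences. At n = 20 this is 2.093 × √(0.0500 + 0.1011) = 0.81. At n = 10 it is 2.262 × √(0.1000 + 0.2134) = 1.27.

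**The case against.** **The validation aim does have a measure.** The Summary sets the aim and the correlation in the same table, so the primary objective is not wholly without a metric. This is fair as far as it goes, but Section 2 ranks that same correlation as secondary, no coefficient is named, and Section 3.5 omits it. A concordance-type coefficient would register bias (it is 0.840 in Case A and 0.774 in Case B), but the plan does not name one.

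**Other evidence is planned.** Section 3.2 simulates sensitivity to changes in oxygenation, and spatial resolution is also an objective. Neither replaces a comparison with the reference, and Section 3.5 does not directly analyse spatial resolution either.

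**Monitoring needs change, not absolute level.** A constant offset would indeed leave changes intact. A slope error would not, and correlation does not detect it. The stated hypothesis is also accuracy.

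**A fixed error can be calibrated away.** It can, but only once its intercept and slope have been estimated, and the plan estimates neither.

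**The illustration is chosen to be striking.** Its inputs are assumptions. The pooled noise-free limits in Case B also run wider than the errors that can occur there, which lie between −15 and +25. That point stands, and it is why limits by level are shown above. The conclusion does not depend on these numbers.

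**The cost may be understated.** Section 3.3 does not say how oxygenation is set or varied in printed resin. If it is not varied, more phantoms or readings would be needed. This stands as a condition on the cost, although the correlation already named would need paired readings at varied levels too.

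**Conclusion.** The concern holds. Followed as written, the plan yields no estimate of measurement error and no criterion for success, so it can neither support nor refute the accuracy hypothesis. That an ordinary correlation ignores offset and scale is certain. The size is illustrative: under the assumed 10–90% range and half-slope error, r of about 0.93 to 1.00 goes with average errors of +25 to −15 points and a halving of true changes. The precision figures further assume one independent pair per MRI. This should be corrected before measurements begin, because a margin chosen after the data are seen would carry little weight.

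**What to change.** **Essential changes**
- *Study Summary and Section 2:* replace correlation with agreement between sensor and reference, and tie it to the primary objective.
- *Section 3.4:* state that sensor and benchtop system read the same phantoms at the same locations and oxygenation levels, in the same units. Give the numbers of phantoms, levels and repeats.
- *Section 3.3:* say how oxygenation levels are set in the phantoms.
- *Section 3.5:* analyse sensor minus benchtop. Report mean bias, 95% limits of agreement with confidence intervals, and calibration intercept and slope. Allow for repeated readings with phantom as a random effect.
- *Criterion:* conclude that the sensor is accurate only if the limits lie within a margin the sponsor fixes before measuring. State whether the point limits or their outer 95% confidence bounds must do so; the bounds are stricter.

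**Worthwhile additions**
- If the error is proportional, let the limits vary with level by regressing the difference on level.
- Show results overall and separately for breast and rectal phantoms, accepting that about 10 pairs each would be imprecise.
- Keep r as a descriptive statistic and name its type.

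**Cost.** Wording in the Summary and Sections 2, 3.3, 3.4 and 3.5, and slightly more analysis. No extra readings are needed if pairing at several oxygenation levels is already planned; otherwise further phantoms or readings would be. The result may look less favourable than a high r.

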1. INTRODUCTION

1.1 BACKGROUND

1.1.1 Tumour Oxygenation

Tissue hypoxia is a common feature of most solid tumours. More than a just simple outstripping of vascular supply, tumour hypoxia results in complex interplay that affects malignant cellular function and the tumour microenvironment. Tumour hypoxia drives a selective pressure towards adaptations for increased cell survival and proliferation as well as angiogenesis. These adaptations are mediated primarily through the Hypoxia Inducible Factors (HIFs): transcription factors that respond to cellular hypoxia through expression of genes responsible for a diverse array of functions including inflammatory cell recruitment, angiogenesis and cell survival. Similarly, hypoxia alters the tumour microenvironment: necrosis attracts tumour associated macrophages (TAMs) and cancer associated fibroblasts, both of which are associated with increased mitogenic and metastatic potential. Angiogenesis in response to tumour hypoxia results in dysfunctional and permeable vessels that provide a route for metastasis.

Tumour hypoxia is chemo- and radio-protective. A wealth of evidence has contributed to the development of the oxygen fixation hypothesis: an understanding that molecular oxygen is a necessary requirement for the mechanistic action of ionizing radiation. Oxygen is required for the generation of free radicals during ionization, and to establish breakages in DNA. Hypoxia is similarly associated with decreased responsiveness to chemotherapy: hypoxia induces changes which reduce susceptibility to DNA damage and induces cell cycle arrest, while localized hypoperfusion reduces chemotherapeutic delivery.

Tumour hypoxia ultimately results in more aggressive tumours with increased metastatic potential and resistance to therapies.

1.1.2 Current Methods of Tissue Oxygenation Monitoring

The potential role for tissue oxygenation monitoring to assist in prognostication, guide treatment decisions and assess responses has driven the need for improved means of assessing tumour oxygenation. The ideal solution would provide accurate, quantitative and continuous assessment of tumour oxygenation, accounting for spatial variation within the tumour.

Eppendorf electrodes provide direct and accurate measurements of tumour oxygenation. However, the invasive nature limits them to superficial tumours, and while providing quantitative assessment of tumour oxygenation, it does not provide a spatial representation of tumour oxygenation.

Positron Emission Tomography with fluorodeoxyglucose (PET-FDG) or oxygen sensitizers such as Fluoromisonidazole or Copper-diacetyl bis(4-methylthiosemicarbazone) provides an indirect spatial representation of tumour oxygenation. It is, however, not quantitative and requires the administration of radioactive isotopes.

Blood Oxygen Level Dependent Magnetic Resonance Imaging (BOLD-MRI) utilises differences in magnetic nature of oxy and deoxyhaemoglobin to provide an indirect assessment of tissue oxygenation. BOLD-MRI detailed spatial assessment of tumour tissue oxygenation without need for agents or isotopes. However, it only provides a snap-shot non-quantitative assessment of tumour oxygenation.

1.1.3 Clinical Paradigms for Tumour Oxygenation Monitoring

Continuous tumour oxygenation assessment is likely to be a valuable adjunct in the management of many cancers. Two paradigms that demonstrate its potential include neoadjuvant chemoradiotherapy for locally advanced rectal cancer, and neoadjuvant therapy for breast cancer.

Rectal Cancer:

The addition of neoadjuvant chemoradiotherapy to transanal mesorectal excision marked a significant advance in the management of locally advanced rectal cancer. 50.4 Gray of external beam radiotherapy given over 28 fractions in conjunction with chemotherapy reduces the risk of circumferential involvement at surgery and improves overall survival. However, the response rates are highly variable, and as low as 30%. The potential benefit is balanced significant costs, with 18% of patients suffering from grade III/IV toxicities. Continuous oxygenation monitoring could provide a useful adjunct in the monitoring of neoadjuvant chemotherapy, potentially allowing for personalisation of management.

Breast Cancer:

Neoadjuvant therapy in breast cancer is used to reduce tumour size, which may convert inoperable tumours to operable ones, allow for breast conserving therapy, and in some cases result in a complete pathological response (pCR). Endocrine therapies, tyrosine kinase inhibitor, and chemotherapy are given alone, or in combination for up to 6 months before surgery. MRI is the preferred modality for assessing response to neoadjuvant therapy and surgical planning, particularly with regards to breast-conserving therapy. However, the diagnostic accuracy of MRI is only 70% and is particularly confounded in cancers with areas of fibrosis. Continuous tumour oxygenation monitoring has the potential to monitor response to neoadjuvant therapy for breast cancer and may provide a valuable adjunct in surgical planning.

1.1.4 Tissue Oxygenation Monitoring Using Diffuse Reflectance Spectroscopy

Diffuse reflectance spectroscopy can measure the oxygenation status of tissue due to the differing absorbance profiles of oxygenated and deoxygenated haemoglobin (Figure 1A). DRS is well suited to oxygenation monitoring as it provides oxygenation measurements that are dynamic (real-time), spatially accurate and quantifiable. Furthermore, it has the potential to be miniaturized into an implantable device.

[figure not shown]

Figure 1: Optical absorbance of oxygenated and deoxygenated haemoglobin.

1.1.5 A Novel Tumour Oxygenation Monitor using DRS

Tumour oxygenation monitoring has the potential to provide valuable insights into tumour prognostication and management. The Institute for Global Health Innovation plans to develop an implantable tumour oxygenation sensor, providing a novel modality for tumour assessment and

monitoring. This research describes the development and validation of oxygenation sensing probe (Figure 2). Successful development and validation of the probe will be followed by future research to miniaturise and incorporate the technology into an implantable device.

[figure not shown]

Figure 2: A tumour oxygenation monitoring probe using diffuse reflectance spectroscopy.

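### The probe is to be called accurate, validated and suitable, but the only sensor-versus-reference measure is a correlation with no acceptance criterion, and Section 3.5 does not analyse it

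*Combined protocol and SAP*

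**What the plan says.** Four places in the protocol call for a judgement on the probe.

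- Section 1.2 hypothesises that the monitor "can provide accurate tissue oxygenation assessment in tumour phantom models".
- The primary objective in Section 2 is "To develop and validate a novel tumour oxygenation monitoring probe which may be used to monitor response to therapies in cancer, using 3D-printed phantoms".
- Section 3.4 says of the phantom work: "The results of these experiments will assess the suitability of the sensor design for monitoring oxygenation in tumours".
- Section 1.1.5 says: "Successful development and validation of the probe will be followed by future research to miniaturise and incorporate the technology into an implantable device".

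The comparison with the benchtop spectrometer, which Section 3.4 names as the reference, is described only as a correlation. The Study Summary gives the outcome measure as "Correlation of sensor oxygenation measurements as compared to gold-standard oxygenation measurements in phantom tissue models", and a secondary objective in Section 2 is "Define the correlation between sensor-derived oxygenation measurements and Gold-standard measured oxygenation in 3D-printed tissue phantoms". No type of coefficient, target value, confidence limit, maximum bias or acceptable error is given.

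Section 3.5 is one sentence. It concerns the share of tumour volume to which the sensor is sensitive, and ends: "the fraction for each tumour will be expressed as a mean+SD summary statistic". It does not mention the comparison with the spectrometer. The 20 scans (10 breast, 10 rectal) are stated without a sample-size calculation, so no margin can be inferred from them.

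**The concern.** There are two linked gaps. First, accuracy is a statement about the size of the sensor's error in oxygenation units, and a correlation coefficient does not measure that. It is unchanged if every reading is shifted by a constant or multiplied by a positive constant. Second, no result is named in advance as good enough, so whether the probe is accurate, validated or suitable would be judged after the data are seen.

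At stake is the study's main conclusion. A probe with a large systematic error could be reported, and under Section 7 published, as validated, and the later miniaturisation work would start from it. The study uses printed phantoms and anonymised scans and treats no patient. The cost is therefore an unsupported claim and misdirected development, not direct harm.

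**Working it through.** **Inputs from the documents.** There are 20 scans (Study Summary, Section 4.1), and the comparison measure is a correlation (Study Summary, Section 2). The documents state no alpha, power, SD, margin or sample-size calculation, so there is no figure of the plan's own to reproduce.

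**Assumptions, not in the documents.** One sensor/reference pair per phantom, so n = 20. In step 1, reference values are evenly spaced from 10 to 90% and random sensor error has SD 3 points. In step 4, the sensor is unbiased and the margin is 20 points.

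**Step 1: does correlation detect a biased probe?** The evenly spaced references have mean 50 and variance 589.5 (divisor n). Simulation of the 20 pairs gave:

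| Probe | r | Mean bias (points) | 95% limits of agreement | Lin's concordance |
|---|---|---|---|---|
| Accurate | 0.99 | 0 | −6 to +6 | 0.99 |
| Reads 20 points too high | 0.99 | +20 | +14 to +26 | 0.74 |
| Reads half the true value | 0.97 | −25 | −50 to 0 | 0.43 |

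A hand check agrees. With an error variance of 9, r ≈ √(589.5 / (589.5 + 9)) = 0.99, with or without the 20-point shift. For the halved probe, r ≈ √(0.25 × 589.5 / (0.25 × 589.5 + 9)) = 0.97. The three probes cannot usefully be told apart by r, but bias and limits of agreement separate them at once.

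**Step 2: how low could a success threshold be?** If success meant only that r differs from zero at two-sided 5%, the critical value is t / √(n − 2 + t²). For n = 20, t = 2.101, so r = 2.101 / √(18 + 4.414) = 0.444, and R² = 0.20. For n = 10 (one tumour type) it is 0.63. Estimation is also loose: an observed r of 0.80 with n = 20 has a Fisher-z 95% CI of 0.55 to 0.92.

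**Step 3: a correlation also depends on the spread of the references.** Take a sensor with error SD 15 points (limits of about ±29) and n = 20. The probability that r exceeds 0.444 is 0.08 if the between-phantom SD is 2 points, 0.28 if it is 5, and 0.96 if it is 15. The same sensor succeeds or fails according to which phantoms are chosen, and the documents do not give that spread.

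**Step 4: what would an error-based rule do?** As an illustration, the probe passes if the one-sided 95% upper bound for 1.96 × root-mean-square error is below 20 points. With 20 independent differences the bound multiplies the observed root-mean-square error by √(20 / χ²(0.05, 20)) = √(20 / 10.85) = 1.358, an inflation of about 36%. The largest observed value that passes is therefore 20 / (1.96 × 1.358) = 7.5 points. The probability of passing is:

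| True error SD (points) | 1.96 × SD | Probability of passing |
|---|---|---|
| 5 | 9.8 | 99.9% |
| 7.5 | 14.7 | 55% |
| 10 | 19.6 | 6% |
| 15 | 29.4 | below 0.1% |
| 20 | 39.2 | below 0.1% |

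**Step 5: precision of limits of agreement.** The 95% CI half-width of one limit is about t × √(1/n + 1.96² / (2(n − 1))) times the SD of the differences. That is 0.81 SD for n = 20 and 1.27 SD for n = 10.

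**The case against.** The strongest reply is that this is an early bench study. Its stated comparison objective is to estimate a correlation, and such work often has no formal test, alpha or sample-size calculation. That is fair, and their absence alone would be a minor complaint. It does not meet the point that the hypothesis and primary objective are about accuracy and validation, which the named measure cannot establish.

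Three stronger readings are tempting and are not supported.

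- A reader might take Section 1.1.5 as a formal go/no-go gate. It is a statement of intent in the background section, and the point does not rest on it.
- A reader might say that no result could count against the hypothesis, or that the plan would pass a poor probe. The plan is silent on a threshold. A null or negative correlation would hardly support accuracy, and a wrong verdict is left possible, not prescribed.
- A reader might quote one pass rate, such as 96% for a probe with error SD 15, as the size of the problem. Step 3 shows that it runs from 8% to 96% over assumed reference spreads of 2 to 15 points.

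It is also fair to object that a margin cannot simply be read off Section 3.2. That section refers to distributions from the literature and candidate regions on the scans, not to one hypoxic-versus-surrounding difference. The sponsor must choose and defend the margin. Finally, an error-based rule is demanding with 20 pairs, as step 4 shows.

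**Conclusion.** The point holds in this form: the protocol promises a conclusion about accuracy, names only a correlation to support it, sets no acceptance criterion, and leaves the comparison out of its statistical section. That correlation is blind to systematic error does not depend on the assumed figures. The size shown does: r of about 0.99 with a 20-point bias assumes references from 10 to 90% and error SD 3 points, and the 0.44 threshold assumes 20 independent pairs. The documents state neither the number of phantoms nor the oxygenation levels or readings per phantom, and repeated readings would change the figures. The change should be made before measurement starts.

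**What to change.** In Section 3.5:

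1. Make the sensor-minus-reference difference, in oxygenation units, the primary validation analysis. Report mean bias, root-mean-square error and 95% limits of agreement, with confidence intervals that allow for repeated readings within a phantom. Report correlation as descriptive.
2. Before any phantom is measured, state a maximum acceptable error, justified by the sponsor from the intended use of the probe.
3. State that the probe is called validated only if the confidence bound for the error lies within that limit, and is otherwise reported as not validated.
4. State how many phantoms, oxygenation levels and readings per phantom will contribute.

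Sections 1.1.5 and 3.4 should refer to this rule for what successful and suitable mean.

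The cost in text is a few sentences and two cross-references. The real cost is that the study can formally fail, and with about 20 independent pairs a probe whose true error is only just inside the margin will usually not pass: 6% at error SD 10 and 55% at error SD 7.5, for the illustrative margin of 20 points. If the sponsor wants a better chance of passing such a probe, more independent pairs may be needed, and that should be settled when the margin is set.
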